3 STUDY DESIGN AND METHODS

3.1 Overall Study Design

The ECSTATIC trial is a two-arm, 1:1 randomized controlled trial, to compare lower (50×10^9 cell/L) and higher (90×10^9 cell/L) platelet thresholds for transfusions in children on ECMO. Eligible and consented participants are to have transfusions managed using the randomly assigned strategy from the time of their randomization until one of five prespecified criteria are met which permanently discontinues the strategy, with allowances for temporary suspension of the assigned protocol as described in the study protocol. Because this is a feasibility trial, analyses focus on the ability to demonstrate adherence to the protocol as captured by separation in the average pre-transfusion platelet counts corresponding to transfusions (Aim 1) and on summaries of ten criteria taken as indicators of the feasibility to conduct a larger trial designed to assess efficacy of the transfusion threshold strategy (Aim 2). The larger trial is proposed to use a novel composite outcome of progression to severe bleeding or severe prognosis (see SE10 in Section 2.2.2 or Section 2.2.3), and added attention is given to the adjudication of this outcome (Aim 3).

3.2 Method of Treatment Assignment and Randomization

This study's randomization scheme is 1:1 allocation to the lower or higher transfusion threshold. Randomization will use random block sizes of 2, 4, or 6, and be stratified by age (≤ 28
days or > 28 days). The randomization sequences will be generated using R version 4.2.1 or later, and the randomization sequences will be loaded to the study's Research Electronic Data Capture (REDCap) database.

3.2.1 Delivery of Randomization and Emergency Backup

When a research coordinator or other designated personnel is enrolling a participant, the study team member will use the randomization module in REDCap to make the treatment assignment. In case of emergency because REDCap is not functioning, each site will be provided one backup randomization envelope containing a treatment assignment. It is very unlikely REDCap will not be properly functioning at the time a patient is enrolled, and therefore one backup envelope per site should be more than sufficient.

3.2.2 Handling of Incorrect Randomization in Study Analyses and Reports

We assume that misrandomization will be rare for this trial. For intention-to-treat analyses, the participants will be analyzed according to the assigned treatment arm, even if it was later determined that the incorrect randomization stratum (defined by age) was used.

3.3 Treatment Masking (Blinding)

The clinical team will be unblinded because they need to know the strategy to which they are to adhere. The Data Coordinating Center (DCC), including the statistical team, will also be unblinded. Otherwise, the steering committee will remain blinded except as needed at their own sites to provided clinical care for participants they are treating. The trial's Data and Safety Monitoring Board (DSMB) will not be blinded.

3.4 Study Intervention Compliance

At the transfusion level, a transfusion is considered to be compliant if it was below the assigned threshold (with the count obtained less than 12 hours previously and not obtained before a prior transfusion) and at the dose level to be used at the local site; it is considered to be non-compliant otherwise (see also SE6 in Section 2.2.2). As a supplementary measure of study compliance, we will distinguish between transfusions that occurred during a period of temporary suspension and those that did not occur during such a period. At the individual level, the person is considered as having been managed in compliance with the assigned treatment if and only if there were no non-compliant transfusions given, ignoring any transfusions given during a period of temporary suspension. Any missed transfusions (i.e., platelet counts below the threshold for which there were no transfusions within 12 hours of the platelet count) are considered as noncompliance. An additional measure of compliance is whether the patient was treated according to institutional protocols for aspects of circulatory support other than the platelet transfusion strategy (e.g., per the site's anticoagulation strategy). The determination of whether local protocols were followed will be made by the study PIs (Drs. [name] and [name]). See also SE9 in Section 2.2.2.

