Patients should not be transfused above the upper transfusion thresholds, i.e., patients should not be transfused for a platelet count $\ge 90 \times 10^9$ cell/L in the higher platelet threshold arm and $\ge 50 \times 10^9$ cell/L in the lower platelet threshold arm. Patients must be transfused below the transfusion thresholds, i.e., patients should be transfused for a platelet count $< 90 \times 10^9$ cell/L in the higher platelet threshold arm and $< 50 \times 10^9$ cell/L in the lower platelet threshold arm and $< 50 \times 10^9$ cell/L in the lower platelet threshold arm. The transfusion should occur within 12 hours of the sample collection time for the platelet count laboratory test. If a platelet count in either direction of the threshold has a platelet count within the next 12 hours in the opposite direction of the threshold (e.g., went from below threshold to not below threshold) without an intermediate platelet transfusion, the earlier platelet count's implied action is superseded by the most recent platelet count to allow sites the flexibility to obtain a confirmatory platelet count in instances where the earlier count is considered unreliable. Specific criteria for temporary suspensions are detailed below.

The **transfusion dose is intended to be 10-20 mL/kg** of apheresis platelets (whole bloodderived platelets may be used if apheresis platelets are not available), which is the median platelet dose reported in two large observational studies (6,20), though adjustments to the dosing to be in line with local implementations are permitted so long as dosing is not differentially applied between assigned transfusion strategies. Though a range of dosing is provided, all doses given at each site will be the same across both arms of the study and will be in line with local guidelines. For patients more than 20-30 kg (per site guidelines), one unit of platelets will be transfused.

For the sites in which the information is available (currently 5 out of the 10 participating sites), the total platelet count (per mL of transfusate) that each patient receives from each transfusion will be recorded. For sites in whom this exact information is not known, we will record if they receive "low-yield" platelet transfusions in which the platelet count is $< 3 \times 10^{11}$ platelets. In addition, we will collect information about irradiation, pathogen reduction and ABO compatibility of the platelet product.

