3. Cryoprecipitate or fibrinogen concentrate (when to measure fibrinogen level or perform viscoelastic testing, what level triggers administration of cryoprecipitate or fibrinogen concentrate, what is the dose, and when to recheck the fibrinogen level)

4. Antithrombin concentrate (when to measure antithrombin level, what level triggers administration of antithrombin concentrate or plasma transfusion, what is the dose, and when to recheck the antithrombin level)

5. Priming of circuit (with plasma, saline, platelets, standard RBC units and/or whole blood)

Data on these co-interventions will be collected daily and compliance with the local guidelines will be measured, so that the effect of any imbalances on the primary outcome can be examined after the trial is complete.

Other co-interventions, such as ECMO flow management, vasopressors, ventilation, red blood cell transfusion, sedation, and the use of hypothermia, will **not be protocolized**, due to the

pragmatic nature of the trial. In addition, the use of other hemostatic agents, such as tranexamic acid, aminocaproic acid, DDAVP, and von Willebrand factor will not be protocolized as these are typically used in patients with active bleeding and not to prevent bleeding (7). However, all these co-interventions will be recorded.

D. Compliance Measures

Patients in the lower platelet threshold arm of the study will be considered adherent to protocol if 90% or more of pre-transfusion platelet counts are $< 50 \times 10^9$ cell/L, and likewise patients in the higher platelet threshold arm of the study will be considered adherent to protocol if 90% or more of pre-transfusion platelet counts are $< 90 \times 10^9$ cell/L.

Should a center have more than 10% of their patients with non-compliant transfusions, we will work with the primary investigator to understand the barriers to following the trial's protocol, and may provide additional measures, such as team education.

In addition to the aforementioned compliance measures, the sixth feasibility criterion pertains to a combined metric of transfusion protocol compliance that considers platelet counts and transfusions. Details of this combined metric are provided in Appendix F.

Measures to Ensure Compliance

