The sixth feasibility criterion's outcome is defined for a combination of platelet-count level and platelet-transfusion-level observations. Adherence is indicated by having an appropriately dosed platelet transfusion within 12 hours after a below-threshold platelet count, and by not having any platelet transfusion when there is no below-threshold platelet count. In general, there is one adherence/non-adherence determination per platelet count (although some are excluded, and some additional determinations can apply when a transfusion occurs without any platelet count in the previous 12 hours).

	,	Platelet Transfusion			
		Yes	Νο	Excluded transfusion(s) was the only transfusion within 12 hours after platelet count ^a	
Platelet count	Yes	Adherence ^{b,c}	Non-adherence ^c	Adherence	
below threshold	No	Non-adherence ^b	Adherence	ignored	
	Excluded platelet count ^d	Non-adherence ^b	ignored	Ignored	

^a Platelet transfusions are excluded if any of the following apply: transfusion start time before randomization or after the time the strategy was permanently terminated; transfusion start time during a period of temporary suspension

^b The transfusion is considered non-adherent if an included (i.e., not excluded) platelet transfusion did not have a below-threshold platelet count as the most recent platelet count, or if there was an absence of a platelet count within 12 hours prior to the transfusion start time, or the most-recent platelet count was at or above the threshold.

^c The platelet count is considered non-adherent if an included (i.e., not excluded) platelet count was below the threshold and there was no platelet transfusion (not known to be at an inappropriate dose) within 12 hours after the platelet count.

^d Platelet counts are excluded if any of the following apply: was more than 12 hours prerandomization; was after the time the strategy was permanently terminated; was prior to randomization, and before randomization had a transfusion and/or another pre-randomization platelet count; was a below-threshold count but within 12 hours after the blood sample was collected, and prior to a subsequent platelet transfusion, there was either a platelet count at or above the threshold or the transfusion strategy was permanently terminated; was a platelet count at or above the threshold but within 12 hours and prior to a blood transfusion, there was either a below-threshold platelet count or the transfusion strategy was permanently terminated.

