Calculation: Adherence % = 100% * (Adherences)/(Adherences + Non-adherences)

Feasibility Criterion 6 Threshold: Adherence > 90%

Statistical Analysis Plan

Protocol Title: ECMO Hemostatic Transfusions in Children

Protocol Version and Date: 1.3.1; July 14, 2023 (BRANY IRB approved July 19, 2023)

SAP Authors: [name] (with reuse of protocol and DCC template language)

SAP Version and Date: 1.0; November 9, 2023

CONFIDENTIAL

Approvals:

Approved By:		
DocuSigned by:	Sutdy PI	
[name]		11/10/2023
N 25066330F4F748A	Title	Date
DocuSigned by:	Study PI	
[name]		11/10/2023
Na891D9374C814C7	Title	Date
DocuSigned by:	Co-I,	
[name]	Statistician	11/10/2023
Nacie D23B98F4BB	Title	Date

Contents

	Abbreviations	v
1	1.1 Purpose of SAP	1 1 1
2	 2.1 Study Objectives	$1 \\ 1 \\ 1 \\ 2 \\ 2 \\ 6 \\ 7 \\ 8$
3	3.1 Overall Study Design	0 0
4	STUDY SUBJECTS AND ANALYSIS POPULATIONS14.1 Eligibility14.2 Populations for Analyses14.2.1 Screening Population14.2.2 Inclusion Population14.2.3 Eligible Population14.2.4 Approached Population14.2.5 Consented Population14.2.6 Intention-to-Treat Population14.2.7 Safety Population1	1 1 1 1 2 2 2
5	GENERAL ISSUES FOR STATISTICAL ANALYSES135.1 Analysis Software135.2 Methods for Withdrawals, Missing Data, and Outliers135.3 Multiple Comparisons and Multiplicity13	$\frac{3}{3}$

	$5.4 \\ 5.5 \\ 5.6$	Planned Subgroups, Interactions, and Covariates	14 14 14
6	INT 6.1 6.2 6.3 6.4 6.5 6.6	CERIM ANALYSES Frequency of and Timepoints for Interim Analysis Stopping Rules for Interim Efficacy Analysis Futility Monitoring in the Interim Analysis Early Trial Termination for Safety Subgroups in the Interim Analysis Blinding in the Interim Analysis	 15 15 15 15 17 17
7	PL 7.1 7.2 7.3 7.4 7.5 7.6 7.7	ANNED ANALYSESDescription of Participant CharacteristicsPrimary Outcome Analysis7.2.1Primary Analysis for Aim 17.2.2Additional AnalysesSecondary Outcomes Analyses (Analyses for Aim 2)7.3.1Primary Analysis for Aim 2Tertiary Outcome AnalysisAdditional Outcome AnalysesTechnical Approaches for Subgroup AnalysesSafety Analyses	 17 17 18 19 19 19 20 20
8	SAI	MPLE SIZE DETERMINATION	21
9	Ref	erences	22
		pendix: INTERIM STOPPING RULE OPERATING CHARACTER- ICS	23
A	Inte	erim stopping rule considerations	23
в			24

Abbreviations

Abbreviation	Definition
AIC	Akaike Information Criterion
APPROACHED	Approached Population; see Section 4.2
BP	Blood Pressure
$\operatorname{CAR}(1)$	Continuous analog of first-order AutoRegressive process

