• Outcome: For each patient in the ELIGIBLE population (see Section 4.2.3), whether the patient was in the APPROACHED population (approached for study participation within 24 hours of cannulation; see also Section 4.2.4)

- Endpoint: $100\% \times (\# \text{ in APPROACHED population}) / (\# \text{ in ELIGIBLE population})$
- Feasibility threshold: > 90%

(SE4) Consent percentage

- Outcome: For each patient in the APPROACHED population (see Section 4.2.4), whether the person was consented to study participation (see also Section 4.2.5 for a description of the CONSENTED population)
- Endpoint: 100% \times (# in CONSENTED population) / (# in APPROACHED population)
- Feasibility threshold: > 50%

(SE5) Randomization of consented patients percentage

- Outcome: For each patient in the CONSENTED population, whether the person was in the ITT population (i.e., consented and randomized; equivalently, in the ENROLLED population; see Section 4.2.6)
- Endpoint: $100\% \times (\# \text{ in ITT population}) / (\# \text{ in CONSENTED population})$
- Feasibility threshold: > 66% (previous data indicate approximately one-third of patients bleed within 24 hours of cannulation)

(SE6) Transfusion compliance rate

• Outcome: This is a transfusion-level outcome for the ITT population, such that some patients could have multiple outcomes and others could have no outcomes. Any transfusions that were performed under a period of temporary suspension will be ignored. Among the remaining transfusions performed between randomization and when the treatment strategy was permanently discontinued, the transfusion will be considered compliant if and only if (a) the most recent nonmissing pre-transfusion platelet count (obtained no more than 12 hours before the transfusion, and not obtained prior to an earlier transfusion) was below the assigned threshold AND (b) the site principal investigators agree the transfusion dose was the proper dose in use at the site (e.g., 10 mL/kg if that is the local guideline and the same guideline applies to each arm of the study); if the pre-transfusion platelet count is not available, it will be assumed that the transfusion was not compliant. Also, if a transfusion was indicated per the threshold (i.e., the platelet count was below the threshold) but no transfusion was given within 12 hours, this will also be considered as an outcome and automatically be regarded as noncompliance

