- Endpoint: 100% × (# of compliant transfusions not during a temporary suspension)/ (# of transfusions not during a temporary suspension + number of transfusions that should have been given but were not)
- Feasibility threshold: >90%

(SE7) Transfusion strategy suspension (not due to preparation for decannulation) percentage

- Outcome: For each patient in the ITT population (see Section 4.2.6), whether the patient had at least one temporary suspension of the transfusion threshold not due to preparation for decannulation before the permanent discontinuation of the treatment strategy. A temporary suspension of the transfusion threshold will not require a transfusion in excess of the threshold to have been given during the suspension period for it to be counted as a suspension
- Endpoint: $100\% \times (\# \text{ in ITT population with at least one temporary suspension of the transfusion threshold not due to preparation for decannulation) / (# in ITT population)$
- Feasibility threshold: < 10%

(SE8) Withdrawal and/or lost-to-follow-up percentage

- Outcome: For each patient in the ITT population, whether the patient was withdrawn from study participation by 90 days post-randomization and/or had an unknown mortality status for the timepoint of 90 days after randomization. The 90-day vital status will be considered known if the 90-day communication for mortality assessment is completed within ± 10 days, inclusive, of 90 days after randomization, or if the patient was known to have already died (e.g., died while on ECMO) such that the 90-day follow-up mortality assessment is unnecessary
- Endpoint: $100\% \times (\# \text{ in ITT population who were withdrawn from the study by 90 days after randomization or had unknown 90-day mortality) / (# in ITT population)$
- Feasibility threshold: < 6%

(SE9) Percentage with any violations of local non-study-specific circulatory support protocols

• Outcome: For each patient in the ITT population, whether the patient had any reported instances of non-adherence to the site's non-study-specific circulatory support strategies. For this outcome, any instances of platelet transfusions above the randomized threshold are immaterial; on the other hand, for example, if the anticoagulation

strategy in place at the site was not followed, this is considered a protocol violation for this outcome. The site PIs will determine whether or not local protocols were followed

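### SAP 3.4 and SE6 score a low platelet count as a missed transfusion even where protocol 1.4 treats it as superseded or cut off by the end of the strategy

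*Combined protocol and SAP*

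**What the plan says.** **SAP 3.4 (Study Intervention Compliance).** A transfusion is compliant if the preceding count was below the assigned threshold, was recent enough, and the dose was the local one. A child is managed in compliance if and only if no non-compliant transfusion was given. The next sentence deals with missed transfusions, defined as "platelet counts below the threshold for which there were no transfusions within 12 hours of the platelet count) are considered as noncompliance". It gives no exception.

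**SAP 2.2.2, SE6.** If a count was below threshold "but no transfusion was given within 12 hours, this will also be considered as an outcome and automatically be regarded as noncompliance". The denominator is transfusions outside temporary suspensions plus the "number of transfusions that should have been given but were not". The feasibility bar is above 90%.

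**Protocol 1.4, section 8.A.** When a count is followed within 12 hours by one on the other side of the threshold, with no transfusion between, the earlier count's "implied action is superseded by the most recent platelet count to allow sites the flexibility to obtain a confirmatory platelet count".

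**Protocol 1.4, Appendix F, footnote d.** A below-threshold count is excluded from adherence scoring if, within 12 hours of sample collection and before a subsequent platelet transfusion, "there was either a platelet count at or above the threshold or the transfusion strategy was permanently terminated". Appendix F describes itself as defining the outcome for the sixth feasibility criterion.

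**Versions.** The SAP is v1.0 of November 9, 2023 and names protocol 1.3.1. The protocol supplied is 1.4 of April 22, 2024.

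**The concern.** Two kinds of low count do not call for a transfusion within 12 hours under protocol 1.4's own scoring: one overtaken by a repeat count at or above threshold, and one whose window was cut short because the strategy ended. The SAP wording scores both as missed transfusions.

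Two measures are affected. SE6 is one of the ten feasibility criteria, of which at least five must be met to support the larger trial. The individual-level compliance measure in SAP 3.4 may be affected too, depending on how that section is read. In both, the error runs one way: it lowers measured compliance for reasons unrelated to adherence. If it is noticed only after the data are in, the choice between the two scoring rules becomes post hoc.

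**Working it through.** The plan states no figure for this point, so there is nothing to reproduce. The check sets the rules side by side and then applies the SAP formula to care that follows protocol 1.4 without error.

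**Step 1. The rules applied to three situations**

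| Situation | Protocol 1.4 (8.A, Appendix F) | SAP 3.4 and SE6 as worded |
|---|---|---|
| Low count at hour 0, count at or above threshold at hour 6, no transfusion | Superseded; excluded | Missed transfusion |
| As above, but transfused after hour 6 | Non-adherent | Non-compliant (most recent count not below threshold) |
| Low count, strategy permanently ended within 12 hours, no transfusion | Excluded | Missed transfusion |

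The documents disagree in the first and third rows and agree in the second. SE6's limit to the period before permanent discontinuation is written for transfusions performed, not for those missed. SAP 5.2 disregards adherence from the time of withdrawal, but no SAP text does the same for decannulation, death, severe bleeding or clotting, day 21, or a suspension longer than 24 hours.

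**Step 2. The SE6 ratio under perfect care**

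Let T be compliant transfusions and S be superseded or cut-off low counts.

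- SAP ratio = T/(T+S). With footnote d's exclusions, S drops out and the score is 100%.
- The criterion is above 90%. T/(T+S) ≤ 0.90 is equivalent to S ≥ T/9.
- With T = 100: S = 11 gives 100/111 = 90.1% (met); S = 12 gives 100/112 = 89.3% (not met).

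**Step 3. Size, on assumed rates**

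The documents give no value for S. Assumptions:

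- 14 counts per child: the twice-daily minimum in protocol 8.A over an assumed 7 days.
- 4.76 transfusions per child: 0.68 × 7, using the historical 68% of ECMO days with platelets (protocol 5.B) and one transfusion per such day.
- A share q of all counts is low and then superseded, so S per child = 14q.

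| q | S per child | SE6 ratio, 4.76/(4.76+S) | Chance a perfectly managed child has at least one such count, 1−(1−q)^14 |
|---|---|---|---|
| 1% | 0.14 | 97.1% | 13% |
| 2% | 0.28 | 94.4% | 25% |
| 5% | 0.70 | 87.2% | 51% |

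The ratio reaches 90% at S = 4.76/9 = 0.53 per child, that is q = 0.53/14 = 3.8%. The last column also assumes independent counts, and it is a rate of children labelled non-compliant only if missed transfusions enter the patient-level measure.

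**Step 4. Strategy endings alone**

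Take 50 children, a share f of whom have one cut-off low count, and m transfusions each. The ratio is 50m/(50m+50f) = m/(m+f).

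| f | m = 2 | m = 8 |
|---|---|---|
| 20% | 90.9% | 97.6% |
| 40% | 83.3% | 95.2% |

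**The case against.** **Version lag.** For criterion 6, protocol 1.4 is the later document and refers the reader to Appendix F, which exempts both cases. A reader might infer that criterion 6 will fail. The documents do not support that: an analyst who follows Appendix F will not meet the problem. What stands is that the SAP still carries a different rule, with no precedence statement or updated SAP in the documents. Appendix F does not reach SAP 3.4, because it is confined to criterion 6.

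**A sensible programmer would get it right.** SE6's denominator speaks of transfusions that should have been given, and under 8.A a superseded count no longer calls for one. That is a fair reading of the denominator, but SE6's outcome text and SAP 3.4 both define the failure by the count alone.

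**Stronger inferences that do not hold**

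- *One superseded count makes the child non-compliant.* The if-and-only-if sentence in SAP 3.4 concerns transfusions given. The following sentence calls missed ones noncompliance without saying at what level. Patient-level scoring is one reading, not a stated rule.
- *Sites would be flagged for remediation.* The trigger in protocol 8.D begins "Should a center have more than 10% of their patients with non-compliant transfusions", and 8.D defines adherence from pre-transfusion counts. A low count with no transfusion produces neither.
- *The higher-threshold arm would suffer more.* Nothing in the documents shows more untransfused low counts in that arm near the end of the strategy. Preparation for decannulation is also a permitted suspension.
- *The SAP alone closes off every compliant action.* Transfusing after a repeat count at or above threshold is non-adherent under the protocol too. The SAP's departure is only in scoring the decision not to transfuse.

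**Limited impact.** The individual-level measure has no threshold or test and does not appear in SAP section 7. Criterion 6 is one of ten, and five suffice. Both points are correct and limit the weight of this one.

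**Conclusion.** The conflict is real on the text. SAP 3.4 and the missed-transfusion sentence in SE6 score as noncompliance two situations that protocol 1.4 excludes, so care that follows the protocol can be marked as a failure.

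The threshold result, S ≥ T/9, follows from the SE6 formula and needs no assumption beyond perfect care. How near the trial would come to it cannot be settled from the documents. On the assumptions shown, SE6 is still met at superseded rates of 1% and 2% and missed at 5%, with the crossing near 3.8%; if such counts are rare the effect is small. The 13%, 25% and 51% figures further require independent counts and the patient-level reading of SAP 3.4.

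For SE6 this is an unreconciled difference between an older SAP and a newer protocol. For SAP 3.4 it is a gap that no other text fills. It should be corrected before analysis; it does not threaten the primary outcome analysis.

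**What to change.** 1. In SAP 3.4 and in SE6, state that a below-threshold count is not a missed transfusion if, within 12 hours of sample collection and before any platelet transfusion, either a later count was at or above the assigned threshold or the strategy was permanently discontinued. This is the substance of Appendix F footnote d; citing Appendix F in both places would also serve.
2. State in SAP 3.4 whether missed transfusions enter the individual-level measure.
3. Name the formula that governs criterion 6. Appendix F also credits correctly withheld transfusions as adherences, whereas the SE6 denominator holds only transfusions given plus those missed. The two percentages can therefore differ even with no superseded or cut-off counts.
4. Update the protocol version that the SAP cites.

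The cost is a few sentences in an SAP amendment. Appendix F already needs the same count, transfusion and discontinuation times, so no new data are required. Only scoring changes; no transfusion rule is altered.
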